The absolute threshold will be the last measured threshold and recorded as the dimmest light that the subject can detect when the rod sensitivity of the study eye is maximum. In a healthy adult, the absolute threshold is typically equal to a logarithmic light intensity around 10^{-6} cd/m^2 at a time of around 30 minutes from the start of the test.

The examiner will monitor in real-time the testing results on a laptop, which is USB-connected to the frame of the goggles from the same side of the study eye. A best fit of collected threshold measurements will be calculated; from this fit, a biphasic curve is expected to be observed.

The rod-cone break will be identified as the point of phase-change in the calculated curve, which coincides with the point when rods become more sensitive than cones. In a healthy adult, the rod-cone break is typically equal to a logarithmic light intensity around 10^{-3} cd/m^2 at a time of around 7 minutes from the start of the test.

The slope of the rod-mediated response will be also calculated from the best fit of the collected threshold measurements. Particularly, the slope of the (second) S2 and (third) S3 rod-mediated component of recovery will be identified: these coincide with a long section of near linear slope following the initial rapid nonlinear increase in rod sensitivity.

An ad hoc pen-and-paper system usability questionnaire will be presented to participants twice upon completion of the first and the last dark-adaptometry testing visit. Participants will rate comfort and ease of use of the system on a scale of 1-10 through questions targeting hardware and software implementation as well as testing duration and expectations.

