4.11. Primary outcomes

Primary outcome variables for Group 1&2:

- Rod-cone break
- Absolute threshold

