Statistical Analysis Plan cover sheet

Wearable Dark-adaptometer in Normal Adult Healthy Volunteers

NCT number NCT02674425

Version 2.0 27/01/2017

WONDER STUDY
Evaluation of a novel wearable light-emitting system for measuring dark-adaptation thresholds in normal adult healthy volunteers

Statistical Analysis Plan

Chief Investigator: [name]
Principal Investigator: [name]
Co-Investigator: [name]
Collaborator: [name]

Clinical Eye Research Centre, St Paul's Eye Unit, Royal Liverpool University Hospital, [name]
University of Liverpool, Department of Eye and Vision Science, Institute of Ageing and Chronic Disease, [name]

Statistical Analysis Plan

Cone- and rod-mediated dark adaptation functions were expressed as log threshold luminance vs. time (minutes). The dynamics of participants' visual recovery after the bleach offset were determined by fitting established models of human dark adaptation to collected threshold data. Two models were used: 1) a bi-exponential model, fitting a single exponential function separately to the cone-mediated phase and the rod-mediated phase of dark adaptation; and 2) an exponential bi-linear model, fitting a single exponential to the cone threshold recovery data and 2 linear components (i.e., S2 and S3) to any rod threshold recovery data.

$$\begin{aligned}
 1) \quad D &= \underbrace{\theta_1 + \theta_2 \cdot \exp\left(\frac{-t}{\theta_3}\right)}_{\text{Cone}} + \underbrace{\eta_4 \cdot \exp\left(\frac{-(t - \theta_5) \cdot h(t, \theta_5)}{\eta_6}\right)}_{\text{Rod}} \\
 2) \quad D &= \underbrace{\theta_1 + \theta_2 \cdot \exp\left(\frac{-t}{\theta_3}\right)}_{\text{Cone}} + \underbrace{\theta_4 \cdot (t - \theta_5) \cdot h(t, \theta_5)}_{\text{S2}} + \underbrace{\theta_6 \cdot (t - \theta_7) \cdot h(t, \theta_7)}_{\text{S3}}
 \end{aligned}$$

$$h(t, \pi) = \begin{cases} 0 & \text{if } t - \pi \leq 0, \\ 1 & \text{if } t - \pi > 0. \end{cases} \quad h(t, \pi) = \frac{1}{(1 + e^{-k(t-\pi)})}$$

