where θ_1 is the absolute cone threshold at time t after cessation of the bleach; θ_2 is the cone coefficient; θ_3 is the time constant of cone recovery referred to as cone τ ; η_4 is the final rod threshold or rod absolute sensitivity; θ_4 is the slope of the second rod phase (S2), which represents the rate limited restoration of photopigment; θ_5 is the rod-cone transition time from bleach offset or α point; η_6 is the time constant of rod recovery; θ_6 is the slope of the final component (S3) of rod recovery; θ_7 denotes the time from bleach offset to the transition between the second and final components of rod recovery, referred to as β point; and h is a switch function as described.

Both models, respectively as in Eq. 1 and Eq. 2, have previously been shown to provide a suitable approximation of cone and rod photopigment regenerations after near total photopigment bleaches [1–3]. Matlab (The MathWorks, Natick, USA) was used to fit the dark adaptation models to collected data.

For the cone-mediated dark adaptation function, a single exponential fit was used to estimate the cone time constant (τ) and cone sensitivity parameters. The cone τ is the time constant of the exponential model and is an estimate of cone sensitivity recovery speed. The cone sensitivity is the plateau of the exponential function and is an estimate of the absolute threshold of cone photoreceptors.

For the rod-mediated dark adaptation function, the parameters of interest were the rod-cone break (RCB), rod slope, and rod sensitivity. The RCB is the time in minutes after bleach offset at which the rods are more sensitive to the test target than the cones. The rod slope is the slope of the sensitivity recovery during the second (S2) and third (S3) components of rod-mediated dark adaptation described by Lamb et al. [4,5]. The rod sensitivity parameter was measured as the minimum sensitivity value of the rod-mediated dark adaptation function around the 40 minutes end of the test.

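### Both SAP models return a rod-cone break for every fitted test, and neither document says when a break counts as not identified

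*Protocol*

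**What the plan says.** Protocol section 4.8 (Dark-adaptometry testing) describes the curve as follows: "A best fit of collected threshold measurements will be calculated; from this fit, a biphasic curve is expected to be observed". The break is then taken from that curve: "The rod-cone break will be identified as the point of phase-change in the calculated curve". In a healthy adult it is said to fall "at a time of around 7 minutes from the start of the test". Section 4.11 lists "Rod-cone break" as one of two primary outcomes.

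The SAP gives the fitted curves: "Two models were used: 1) a bi-exponential model, fitting a single exponential function separately to the cone-mediated phase and the rod-mediated phase", and 2) a model with an exponential cone term and two linear rod components, S2 and S3. Both contain θ5, which "is the rod-cone transition time from bleach offset or α point". Matlab is named as the fitting software. Starting values, parameter bounds and a convergence rule are not given.

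The SAP then compares cone and rod parameters with published data. It computes the repeatability coefficient (RC) and within-case coefficient of variance (wCV) for participants with at least two visits, and an intra-class correlation coefficient (ICC) for each age group.

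**The concern.** The study aims to show that a new device generates full dark-adaptation functions, so whether a recording contains two phases is part of the question. Yet the break is read from a curve whose formula already includes a break time. A test that recorded only one phase would still be given a value for a primary outcome.

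The documents leave room for such tests. The bleach is a camera flash directed at the eye, after which the participant pulls the goggles down, and no check that the bleach was adequate is described. The SAP justifies its models for near-total bleaches. Its wording for the second model allows that rod data may be absent, but no rule follows.

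At stake are research questions I (agreement with the literature) and III (repeatability). The SAP does not list the measurements that enter RC, wCV and ICC; I take the primary outcomes to be among them.

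**Working it through.** The documents give no figure to reproduce on this point. The check has five steps.

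**1. Is a one-phase curve inside the models?** The SAP's equations are

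- Eq. 1 (six parameters): D = θ1 + θ2·exp(−t/θ3) + η4·exp(−(t−θ5)·h(t,θ5)/η6)
- Eq. 2 (seven parameters): D = θ1 + θ2·exp(−t/θ3) + θ4·(t−θ5)·h(t,θ5) + θ6·(t−θ7)·h(t,θ7)

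Put η4 = 0 in Eq. 1, or θ4 = θ6 = 0 in Eq. 2. Each becomes D = θ1 + θ2·exp(−t/θ3) whatever θ5 is, for either printed form of h. Numerically, the residuals were identical at θ5 = 2, 7, 20 and 33 minutes. With one-phase data θ5 is therefore not identified, but the fit still reports a number.

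**2. Is there a rule to catch this?** Protocol sections 4.8, 4.11 to 4.14 and the SAP contain no one-phase comparison, no minimum size for the rod term, no precision limit on θ5 and no category for an unidentified break.

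**3. What do the fits return?** Simulation by bounded least squares, step form of h. The test length and starting luminance follow the protocol (25–35 minutes, of which 35 was used; 4.86 cd/m²). Assumed: 35 or 70 thresholds, noise SD 0.1–0.2 log unit, θ5 bounded to 0.5–34 minutes, optimiser starts at 3, 7, 12, 18 and 25 minutes, 60–100 replicates per setting. The break-free curves were a cone-only exponential, single exponentials falling to about −6 log cd/m² (time constant 5 or 10 minutes), and a straight line.

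| Data | Fit | Result |
|---|---|---|
| True break at 7 min | best of five starts | median θ5 7.0–7.1 min (Eq. 2), 8.2–8.7 min (Eq. 1) |
| No break, exponential | best of five starts | θ5 returned in 100%; medians about 5 to 23 min; 2–34% within 5–9 min |
| No break, exponential | one start at 7 min | 0–66% within 5–9 min |
| No break, exponential | one start at 18 min | 0–22% within 5–9 min |
| Straight line | best fit | 27–43% (Eq. 2) and 0% (Eq. 1) within 5–9 min |

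For reference, a θ5 spread evenly over the bounds would fall within 5–9 minutes in 4/33.5 = 12% of tests.

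The starting value matters. For a single exponential with time constant 5 minutes, 35 thresholds and Eq. 2 with free slopes, median θ5 was 2.5, 4.6 and 13.8 minutes from starts at 3, 7 and 18 minutes. Taking the best of five starts gave 9.9 minutes (interquartile range 3.7–20.3).

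**4. Does a one-phase comparison help?** In the same simulation, the small-sample Akaike criterion (AICc) preferred the single exponential in 90–100% of exponential break-free tests and in 0% of true two-phase tests. It caught 0% of straight-line declines. Separate grid-search fits (80 tests per scenario, thresholds over 33 minutes) required AICc to be lower by more than 2 for the two-phase model. False breaks fell to 0–6%. True breaks were kept in 85–89% of tests with 30 thresholds and SD 0.2, 99% with 30 and SD 0.15, and 100% with 60 and SD 0.2.

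**5. What could a few such tests do to RC?** Full follow-up gives 20 × 3 = 60 tests. Assume a within-subject SD of 1 minute for true breaks, and unidentified values with the same mean and SD 6 minutes. RC = 1.96 × √2 × SD = 2.77 × SD.

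- None unidentified: variance 1, RC = 2.8 min
- 5% (3 tests): variance 0.95 × 1 + 0.05 × 36 = 2.75, SD 1.66, RC = 4.6 min
- 10% (6 tests): variance 0.90 × 1 + 0.10 × 36 = 4.5, SD 2.12, RC = 5.9 min

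**The case against.** *The models can show a one-phase result.* Step 1 proves it. In the grid-search fits without sign constraints, only 41–61% of break-free tests gave a downward break, so 39–59% would visibly lack the expected shape. This stands. A reader might infer that the biphasic expectation is a check that cannot fail, and the documents do not support that. Section 4.8 states an expectation, not a check, and a fitted curve can look monophasic. What is missing is any rule for what happens to θ5 when it does.

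*Break-free data are hypothetical.* The protocol's background describes two phases in normal eyes, and the SAP cites earlier support for both models. This also stands: the simulated curves are assumptions. But demonstrating the two phases with this device is the purpose of the study.

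*Other safeguards exist.* The examiner watches results in real time, raw points are kept, and the Steering Committee sees first-visit plots. The second primary outcome does not depend on the break: "The absolute threshold will be the last measured threshold". A cone-only recording would probably show there. These help, but none carries a criterion for the break.

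*Restricting the analysis to identified breaks could flatter the device.* Dropping the noisiest tests from a repeatability study would do so. This stands and shapes the fix.

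**Conclusion.** The gap is real and of moderate weight. Both models yield θ5 for every fitted test, the primary outcome is read from the fitted curve, and nothing in either document separates a supported break from an arbitrary one. The algebra rests on no assumption beyond the printed equations. The percentages rest on assumed curves, noise and numbers of thresholds, and only the step form of h was simulated. The RC figures are an illustration, not a forecast, because the frequency of unidentified breaks is unknown.

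A reader might also infer that spurious breaks gather near the expected 7 minutes and so imitate agreement with the literature. The evidence does not support that. With a full search, 2–34% of exponential break-free tests fell within 5–9 minutes, against 12% for an even spread. Higher shares, up to 66%, came mostly from starting the optimiser at 7 minutes. Where a spurious value lands depends on settings that the SAP leaves open.

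**What to change.** In the SAP, with a cross-reference in protocol section 4.8:

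1. For every test, also fit D = θ1 + θ2·exp(−t/θ3) to the same thresholds.
2. Call the break identified only if the two-phase model is better by a pre-stated criterion (for example AICc lower by more than 2), the fitted rod term falls, and θ5 has a bounded confidence interval. The last two conditions are there because AICc against a single exponential can miss a straight-line decline; their performance was not simulated here.
3. State the starting values and bounds for all fits.
4. Report the number and share of tests with an identified break by age group and visit. This is the evidence that the device yields a biphasic function.
5. Report the rod-cone break summary, literature comparison, RC, wCV and ICC for all tests and for identified breaks only, side by side. Keep the all-tests repeatability result as the main one.

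The cost is SAP wording and one extra three-parameter fit for each of about 60 tests, on thresholds already stored as .csv files. Some true breaks in noisy tests would be marked not identified (11–15% with 30 thresholds and SD 0.2 in step 4, on the AICc rule alone); the all-tests results keep them in view.

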4.9. Study schedule

Table 1 shows the schedule for each group of participants.

Table 1 Healthy adult volunteers schedule (Group 1 & 2)

Study Phase	Screening	Inclusion	Follow-Up Phase		
			Testing Phase	Testing Phase/Exit	
Visit	Screening	Baseline W0	W1-W3		
Min. window (in days) after each testing phase	N/A	0	N/A	1	1
Procedures					
Informed consent	X				
Medical history, family history and demographics	X				
Inclusion/Exclusion criteria	X	X			
Ocular History		X			
Refractive error		X			
DVA		X			
SKILL card		X			
Contrast sensitivity		X			
Pupillometry		X			
Confrontational visual fields		X			
Direct ophthalmoscopy		X			
Psychomotor capability		X			
Dark-adaptometry testing			X	X	X
Usability questionnaire			X		X

The end of the trial will be defined as the last dark-adaptometry testing visit of the last participant, followed by the collection of the 2nd system usability questionnaire.

4.10. Recruitment

Group 1 & 2

The PI will recruit healthy adult volunteers with no prior or current eye problems and good general health. They will be recruited from University of Liverpool students and staff, Royal Liverpool University Hospital students, and people accompanying patients attending St. Paul's Eye Unit.

Baseline examination takes place in general ophthalmology clinics of St. Paul's Eye Unit at Royal Liverpool University Hospital. Subjects deemed eligible for the study will be recruited after signing a detailed informed consent if they meet the inclusion criteria.

4.11. Primary outcomes

Primary outcome variables for Group 1&2:

- Rod-cone break
- Absolute threshold

4.12. Secondary outcomes

Secondary outcome variables for Group 1&2:

- Slope of the (second) S2 component of rod-mediated recovery
- Slope of the (third) S3 component of rod-mediated recovery
- Mean difference between corresponding threshold measurements, which are significant for shaping the dark-adaptation function, obtained at each dark-adaptometry visit;
- Score of the questionnaire used to assess participants' comfort and ease of use of the novel light-emitting system.

Based on the results, several correlations between primary and secondary outcomes will be investigated in each group.

4.13. Data collection/Project management

Anonymised data will be collected by the PI and stored in accordance with the Data Protection Act and data governance protocols of the University of Liverpool and Royal Liverpool University Hospital. A clinical database will be arranged by the PI and held for a period between 6-12 months into a locally installed electronic data recording system at the Clinical Eye Research Centre of St. Paul's Eye Unit, Royal Liverpool University Hospital.

A Project Steering Committee will meet at the beginning and at the end of the investigation. In addition to these meetings they will be issued with information about the real-time data collected by the PI when all recruited participants will have undergone at least one dark-adaptometry testing visit. The committee will evaluate system performance and variability of collected data based on the real-time plots recorded by the PI during the first dark-adaptometry visit. In the event that the assumptions underlying the sample size calculation are seen to be incorrect at the time of the interim analysis, they will have the option to advise further recruitment to the study.

Data variables:

Refractive error (-5÷0÷5 dioptres – spherical; 0÷3 – cylinder)

DVA (letters)

Low-luminance NVA (letters)

Contrast sensitivity (letters)

Pupil size (mm)

Visual field

Fundus

Data collected during the dark-adaptometry testing visits will be in the form of a “log threshold intensity vs time” plot together with a .csv file including a list of the data points.

4.14. Data analysis

Data analysis will be performed by the PI and reviewed by this study team members.

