Dark-adaptometry testing will be carried out by using the novel investigational system described in Section 4.3. Wearable goggles and joystick are given to participants in their switched-on status and held by the subject under test respectively on the forehead, with an elastic strap, and on the dominant hand. For hygienic safety purposes, a non-allergenic disposable tissue will be placed on top of the inner gasket of the goggles that will be in contact with participants' face. Where a disposable tissue would not be available, the inner gasket of the goggles will be accurately cleaned with a sterile isopropanol solution. Participants will sit comfortably throughout the test and wear disposable earphones playing music to drown out external noise and any auditory signals from the embedded electronics when light stimuli are emitted. Testing is non-invasive and is semi-automatic in that the subject under test is required to collaborate actively during the procedure in order to start it and go through it. A responsible collaboration throughout the test will be repeatedly encouraged as testing results are strictly based on the subject's response. The examiner will start the test by triggering a white flash of light through a standard camera flash (e.g., Canon Speedlite 540EZ – Guide Number 54, 1.2 ms duration). The flash will be channelled to the study eye and aims to photo-bleach, hence reset the photoreceptors of the retina. Immediately after the onset of the photo-bleaching flash, the goggles are pulled down over the eyes by the user that will now be exposed to intermittent white light stimuli. Light stimuli are shone automatically inside the goggles after the photo-bleaching flash and until the end of the test. Dark-adaptometry testing will last for about 25-35

minutes and will involve one eye only. This will be randomly allocated by the examiner or will be the only eye meeting the inclusion criteria. As the brightness of the intermittent light stimuli changes throughout the test as well as the time at which they are presented, participants are asked to press either of the joystick's buttons to indicate when the light is visible. The intermittent light features an initial brightness of approximately 4.86 cd/m^2 and becomes dimmer and dimmer overall. The test lasts until participants will not be able to identify any new light stimuli.

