4.15 Adverse event reporting

All adverse events, whether related to the investigational system or not, will be recorded fully and all serious adverse events will be reported in accordance with regulation 16(10)(a) of the

Medical Devices Regulations 2002 (SI618) and Annex X of the Medical Devices Directive 93/42.

The PI will monitor the dark-adaptometry examination in real time and terminate it if a safety signal is identified and considered to be significant.

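### No masking of the curve fits is described, although the PI who monitors the tests also analyses them and some fitting choices are left open

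*Protocol*

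**What the plan says.** The protocol gives the PI four roles:

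- Recruitment (section 4.10): "The PI will recruit healthy adult volunteers with no prior or current eye problems and good general health".
- Data collection (section 4.13): "Anonymised data will be collected by the PI and stored in accordance with the Data Protection Act".
- Live monitoring (section 4.15): "The PI will monitor the dark-adaptometry examination in real time and terminate it if a safety signal is identified and considered to be significant".
- Analysis (section 4.14): "Data analysis will be performed by the PI and reviewed by this study team members".

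Section 4.8 adds: "The examiner will monitor in real-time the testing results on a laptop". It also states the expected result beforehand: "from this fit, a biphasic curve is expected to be observed", with a rod-cone break near 7 minutes and 10^-3 cd/m^2, and an absolute threshold near 30 minutes and 10^-6 cd/m^2, in a healthy adult.

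The SAP fits two models in Matlab: a bi-exponential one, and a cone exponential with two linear rod components. It compares the fitted parameters with published data, giving particular weight to a study of ageing by decade. It reports a repeatability coefficient (RC), a within-case coefficient of variation (wCV) and an average-measure intra-class correlation (ICC) for each age group.

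The text available mentions no masking of the person who fits the curves. Section 4.16 (study personnel) is listed in the protocol's contents but was not in that text, so it could not be checked.

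**The concern.** Test-retest statistics are informative only if each visit is read independently of the others. Someone who has watched visit 1, knows the participant's age group and knows the published value can, without intending to, settle an open fitting choice in the direction that looks right.

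Two of the study's main questions are exposed: whether the results are repeatable, and whether they match the literature, including in the older group. A pull towards expectation would flatter the device on both, and nothing in the reported statistics would reveal it.

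**Working it through.** The plan gives no figure to reproduce here: it states no within- or between-participant SD and no target for RC or ICC. The check is therefore a comparison of what the documents fix with what they leave open.

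**1. Could the analyst know visit and group?** By role, yes. The person named for analysis also recruits, collects the data and monitors the tests, and section 4.13 has the PI recording the real-time plots of the first visit. Anonymised storage protects participants' identity. It does not hide visit or group from the person who ran the visit.

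**2. What is already mechanical?** The goggles set stimulus intensity and timing, and emission stops once the absolute threshold is reached (section 4.3). Points are written to a .csv file, and software does the fit.

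**3. What stays open, by outcome?**

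- *Absolute threshold (primary).* The protocol takes the final threshold recorded. The SAP takes the minimum near the 40-minute end of the test. The definitions differ and should be aligned, but each leaves little room for judgement.
- *Rod-cone break (primary).* Both models contain a rod-cone transition time, theta_5, and the SAP does not say which model supplies the reported value. Two forms of the switch function h are printed, a step and a logistic, with no rule for choosing and no value for k. For the bi-exponential model the SAP describes separate fits to the cone and rod phases, without saying how points are assigned to a phase.
- *S2 and S3 slopes (secondary).* Only the second model yields these, so model choice does not arise. The switch function, starting values and bounds do.
- *All fitted parameters.* There is no rule for excluding points, for starting values or for a fit that fails.

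**4. Which way would an unmasked choice push?** RC = 1.96 x sqrt(2) x s_w = 2.77 x s_w, where s_w is the within-participant SD.

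- If choices at visits 2 and 3 lean towards the same participant's earlier curve, s_w falls. RC and wCV fall in proportion, and ICC rises.
- If choices lean towards a published value, the apparent offset from the literature shrinks. The effect on ICC is then unclear, because spread between participants shrinks too.

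**5. How many curves?** Two groups of 10, three visits, one eye: 20 x 3 x 1 = 60 at most.

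**6. Size.** It depends on how often, and how far, open choices follow expectation. The documents say nothing about that, so no figure is given.

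**The case against.** The strongest case against has five parts.

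- *The unmasked fitting is inferred.* No sentence says the PI fits curves with visit and group in view. This stands. The point rests on combined roles and the absence of a described masking step, and a masked reader named in section 4.16 would weaken it.
- *Automation leaves little to judge.* This stands in part. It largely clears the absolute threshold. A reader might also infer that the cone/rod split is made by hand. The equations do not support that as the only reading, because theta_5 is a parameter to be estimated. The SAP's reference to separate fits leaves a manual split possible, and the other open choices remain.
- *There is review already.* Team members review the analysis, and the steering committee sees first-visit plots. Both count for something, but neither is described as masked or as an independent refit.
- *Locking the fitting rules would do most of the work.* Probably true, and it is half of the fix. Coding the files adds protection wherever a rule cannot foresee a case.
- *Prompting cannot be shown to follow the plot.* Section 4.8 says: "A responsible collaboration throughout the test will be repeatedly encouraged as testing results are strictly based on" the participant's responses, and the examiner sees the live results. A reader might infer that encouragement is steered by the curve. Nothing says so, and participants wear earphones playing music, which makes it less plausible.

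**Conclusion.** The point holds as a risk that is cheap to remove. One person holds the recruiting, collecting, monitoring and analysing roles, no masking of the fits is described, and enough fitting choices are open that repeatability and agreement with the literature could look better than they are. The exposure lies mainly in the rod-cone break and the S2 and S3 slopes, and much less in the absolute threshold.

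A reader might go further and conclude that the fits were made with earlier results in view, that the estimates are biased, or that the bias has a known size. The documents support none of these. A simulated size would have to assume how strongly choices follow earlier curves, and would only return that assumption. Nor is the sensitivity of the rod-cone break to where the phases are split a measure of missing masking: a masked analyst who applied one common split would be affected in the same way.

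The conclusion assumes that section 4.16 names no masked reader and that the PI makes the fits, as section 4.14 implies.

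**What to change.** Add a paragraph to section 4.14 and to the SAP:

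1. An existing team member other than the PI replaces participant, visit and group identifiers in the .csv files with random codes and keeps the key.
2. Before any coded file is fitted, one script is locked. It states the model that supplies each outcome, the form of the switch function (with k if logistic), parameter bounds, starting values, the point-exclusion rule and the handling of failed fits.
3. The script estimates the rod-cone transition for each curve. It does not impose a common split, which could itself lower apparent variability.
4. All curves, at most 60, are fitted in random order, and the results are frozen before the key is opened.

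The PI's live safety monitoring and the steering committee's look at first-visit real-time plots need no change, because coding applies only to the files used for fitting. Optionally, section 4.8 could standardise the wording and timing of encouragement, since later coding cannot undo anything that happens during a test.

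The cost is a small amount of file handling by existing staff and a short wait before analysis. One limit remains: the PI may recognise an unusual curve from memory. Random order and a locked script leave little scope to act on that.
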